Number	Date	Section of study protocol	Amendment	Reason
6	Jan 2015	9.3.2.1 9.7.2 9.7.2.1	Addition to section on bleeding definition Addition to section on renal failure definition Addition of section to handle missing data	Response to PRAC review
5	Nov 2014	8.2 9.3.1 9.7.1 9.7.2.1 Annex 3	Additional variables for patient characterisation and analyses thereof; strengthened analyses of renal impairment. Table 12, ICD codes related to renal impairment added	Response to PRAC review
4	May 2014	General	Extension of study timelines. Comparator updated for acute coronary syndromes. Added secondary safety outcome: "other bleeding" Transfer to EMA protocol template. Label wording updated. Current protocol is V5.0.	PRAC request
3	Mar 2012		Inclusion of additional indication, treatment of pulmonary embolism. V4.0 of protocol.	Label expansion
2	Dec 2011		Inclusion of additional indication, acute coronary syndrome. V3.0 of protocol submitted with EU RMP V	Label expansion

			7.1	
1	Apr 2011		Inclusion of additional indication, stroke prevention in atrial fibrillation. V2.0 of protocol submitted with EU RMP V 6.1.	Label expansion

6 Milestones

Table 2: Milestones

Milestone	Planned date
Start of data collection (Marketing Authorization granted for DVT treatment)	Q1 2012
Interim report 1 2 years drug utilization data and crude incidences for primary safety outcomes	Q4 2015
Interim report 2 4 years drug utilization data and crude incidences for primary safety outcomes	Q4 2017
End of data collection	Q4 2018
Final data availability	Q4 2019
Progress reports	Annual in November 2014–19
Final report of study results with full outcomes analysis	Q4 2020
Registration in the EU PAS register	Study to be registered after PRAC approval

7 Rationale and background

Rivaroxaban, a direct Factor Xa inhibitor, is licensed for multiple indications:

- The treatment of deep vein thrombosis (DVT) or pulmonary embolism (PE), and prevention of recurrent DVT and PE in adult patients (DVT/PE treatment) (15 mg rivaroxaban twice daily [bid] for 3 weeks, then 15 mg or 20 mg once daily [od]).
- The prevention of stroke and systemic embolism in adult patients with non-valvular atrial fibrillation (stroke prevention in atrial fibrillation [SPAF]) with one or more risk factors, such as congestive heart failure, hypertension, age \geq 75 years, diabetes mellitus, prior stroke or transient ischaemic attack (20 mg rivaroxaban od).

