9.2 Setting

Study drug users will be selected from the outpatient pharmacy database. This database records all outpatient dispensings from primary and secondary care in a well-defined geographic area. All study drug users living in this area will be captured in the database. All patients aged 2 years and above who have been registered in the database for at least 1 year before the index date will be included. A sub-population will be defined of patients for whom GP recorded information is also available.

The enrolment period will start on December 10, 2011 (the day after rivaroxaban received first marketing authorization in the Netherlands for the ‘treatment of DVT and long-term secondary prevention of recurrent DVT and PE’). End of enrolment will be 31 December 2017 and end of follow-up will be 31 December 2018. Interim reports will be provided for data collected 2 and 4 years after the date that rivaroxaban receives reimbursement approval for DVT treatment (see [Section 6](#) for detailed milestones). The characteristics of the two study cohorts in the first year and subsequent years of the enrolment period will be compared.

The drug utilization analysis ([Section 8.1.1](#)) will be performed in the sub-population captured by both the outpatient pharmacy database and the GP database, in order to enrich the data for the assignment of indication of use.

The Adverse Outcomes analysis (Sections [8.1.2](#) and [8.2](#)) will be performed in the full rivaroxaban cohort (outpatient pharmacy database with outcomes available from Medical Register), using the dosing as a proxy for the indication when this information is not available, and in the subcohort of comparator drug users captured by both the outpatient pharmacy database and the GP database.

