9.5 Study Size

All patients registered in the PHARMO outpatient pharmacy database and meeting the inclusion criteria will be included. The size of the population receiving rivaroxaban will be dependent on market uptake across the indications of interest (DVT/PE treatment, ACS and SPAF).

According to a preliminary sample size calculation, based on an incidence of haemorrhagic stroke in vitamin K antagonist-treated patients of 5 per 1000 person-years, 12,000 rivaroxaban-treated patient-years and 48,000 vitamin K antagonist-treated patient-years would be required to exclude a 50% increased risk of haemorrhagic stroke in rivaroxaban-treated patients compared with vitamin K antagonist-treated patients with a power of 80%.

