9.7.2 Safety and effectiveness outcomes

The two cohorts (of first-time users of rivaroxaban and first-time users of standard of care) will be followed up from the index date until 12 months after the end of the enrolment period for potential outcomes (safety and effectiveness). For each outcome, the first hospitalization for that outcome during the follow-up period will be identified. A separate follow-up will be performed for each of the outcomes.

For all outcomes (for DVT/PE treatment, SPAF and ACS), crude incidence rates will be estimated in both cohorts, using an as-treated approach. In this, person–time will be categorized into current, recent, past and non use. Current use will refer to person–time up to 7 days after the end of supply of the index drug, recent use will refer to person–time up to 90 days after the end of current use, past use will include all person–time contribution after the end of recent use up to 1 year after the end of current use, non-use will include all remaining time person–time contribution after past-use until end of follow-up.

Age- and sex-adjusted rate ratios with 95% CIs will be estimated for each of the three adverse outcomes comparing rivaroxaban with standard of care using Poisson regression analysis. Where numbers and data permit, adjustment will be made for relevant co-medication (described in the drug utilization section), indication and previous hospitalization for bleeding.

As a general strategy, no data imputation strategies will be applied to supplement missing data. The requirement for inclusion is complete data for critical variables such as exposure to rivaroxaban or standard of care and hospitalizations for bleedings or any other outcome event; otherwise this individual is not eligible to be a member of the study population. However, missing values may occur for potential confounder or effect modifying variables. In this case, individuals with missing values will be kept in the analysis and a separate category will be created for missing values of that variable. In sub-analyses to evaluate confounding or effect modification by variables with a large proportion of missing values, the evaluation will be considered to be conducted on the subset with complete data for the variable of interest.

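### The Poisson rate ratio makes no allowance for time since treatment start, so unequal length of use between the cohorts can bias it in either direction

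*Protocol*

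**What the plan says.** Protocol section 9.7.2 estimates rate ratios for the three primary bleeding outcomes, "comparing rivaroxaban with standard of care using Poisson regression analysis. Where numbers and data permit, adjustment will be made for relevant co-medication". Age and sex are always in the model. The conditional list in full is that "adjustment will be made for relevant co-medication (described in the drug utilization section), indication and previous hospitalization for bleeding". The abstract gives the Poisson comparison with age and sex only, based on person-time.

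Section 9.7.2 classifies person-time as current, recent, past or non-use. "Current use will refer to person–time up to 7 days after the end of supply of the index drug"; the other three categories follow in sequence from there. The classification is introduced for the crude incidence rates. The sentence on the rate ratio does not say which category or categories it uses.

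Section 9.2 sets one closing date for everyone: "End of enrolment will be 31 December 2017 and end of follow-up will be 31 December 2018". Section 9.5 says of accrual: "The size of the population receiving rivaroxaban will be dependent on market uptake across the indications of interest".

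Section 9.7.2.2 plans sensitivity analyses around starting and stopping treatment, because the drugs act differently. It adds that biases noticed in the utilization data can be dealt with in the outcome analyses. It gives no method.

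**The concern.** A Poisson model without a time term treats the bleeding rate as constant across the person-time it pools. Enrolment opens in December 2011, so one patient's current use could run from the first week to about seven years, all in one band. A cohort with shorter use has a larger share of its person-time soon after the start. If the hazard is higher (or lower) early, in the same way for both drugs, that difference in mix enters the drug coefficient.

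There are reasons to expect the lengths to differ. Follow-up closes on a common date while rivaroxaban accrual depends on uptake. Indication affects duration, but adjustment for it is conditional. Supply is also measured differently: section 9.3.1 says dose is not available for vitamin K antagonists (VKA), and section 9.9 names misclassification of VKA exposure as a limitation.

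At stake is the interpretation of the main safety result. A confidence interval around a ratio biased in this way does not show the problem, and the result could be too alarming or too reassuring.

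**Working it through.** **1. The plan's own figure.** Inputs from section 9.5: 5 events per 1000 person-years, 12,000 rivaroxaban and 48,000 VKA patient-years, an increase of 50% to be excluded, 80% power. The 95% interval implies two-sided 5%.

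- Expected events: 12,000 × 0.005 = 60 and 48,000 × 0.005 = 240.
- SE(log RR) = √(1/60 + 1/240) = 0.144.
- Power = Φ(ln 1.5 / 0.144 − 1.96) = 80.2%.

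The stated size is reproduced. It assumes one constant rate per cohort.

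**2. Size of the bias.** Let the hazard in an early window be k times the later hazard, equally for both drugs (true ratio 1 throughout). Let f₁ and f₀ be the shares of rivaroxaban and comparator person-time inside that window. Then

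spurious RR = [1 + (k − 1)f₁] / [1 + (k − 1)f₀].

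This is exactly 1 if k = 1 or f₁ = f₀.

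**3. Assumed inputs, none of them in the documents.** k = 3; early window 21 or 90 days; current use ends exponentially; rivaroxaban entry rises and VKA entry falls linearly over enrolment; planned person-years.

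| Early window | Median use, rivaroxaban vs VKA (years) | Spurious RR | 95% CI excludes 1 |
|---|---|---|---|
| 21 days | 2 vs 2 | 1.015 | 5% |
| 21 days | 1 vs 2 | 1.04 | 6–7% |
| 21 days | 0.5 vs 2 | 1.11 | 12% |
| 90 days | 2 vs 2 | 1.05 | 7% |
| 90 days | 1 vs 2 | 1.15 | 18% |
| 90 days | 0.5 vs 2 | 1.34 | 61% |
| 90 days | 2 vs 0.5 | 0.80 | 28% |

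For 90 days and 1 vs 2 years, k = 2 gives 1.08 (9%) and k = 5 gives 1.26 (41%).

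*One row by hand (90 days, 1 vs 2 years, k = 3).* The simulated early shares are 19.5% and 10.4%, so RR = (1 + 2 × 0.195)/(1 + 2 × 0.104) = 1.390/1.208 = 1.15. Events are 60 × 1.15 = 69 and 240, so SE = √(1/69 + 1/240) = 0.137. The chance of excluding 1.5 is Φ((ln 1.5 − ln 1.15)/0.137 − 1.96), about 50% instead of 80%.

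*Same durations, 21-day window.* RR = 1.04, events 62.4 and 240, SE = 0.142, and the same formula gives about 73%.

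**4. Check with a simpler persistence model.** With exponential use and no calendar cut-off, the share in the first quarter-year is 1 − exp(−0.25/mean). Means of 1 and 2 years give 0.221 and 0.118, so with k = 3 RR = 1.442/1.235 = 1.17. Means of 1.5 vs 0.5 years give 0.73. With a lower early hazard (k = 0.5), 0.5 vs 1.5 years gives 0.87. Both directions are possible.

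**5. Does a time term cure it?** Over 1,000 simulated data sets per scenario under the step 4 model, an early/late factor in the Poisson model returned the ratio to 1.00 for means of 1 vs 2 years (k = 2 and k = 3). With k = 3 the chance of excluding 1.5 rose from 47% to 86%. This is above 80% because the larger early share produces more than 60 rivaroxaban events. When the hazard was in fact constant (k = 1, means 0.5 vs 1.5 years), the chance went from 80.9% to 78.9%, so an unneeded term costs little.

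**The case against.** The strongest reply is that this argues from silence. Section 9.7.2 gives no model equation, and the splitting of person-time is often settled in a statistical analysis plan, which is not at hand and might contain it. That would repair the analysis. But the protocol does name the model and its adjustment variables, and time since start is not among them. Item 5.5 of the Annex 2 checklist, on dose- or duration-dependent response, is marked not applicable.

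The second reply is section 9.7.2.2. Dispensed amounts will be collected, so unequal duration will be visible and could be handled. This stands in part. The planned analyses, however, concern differences between the drugs in mode of action, not a time pattern they share. They leave the main ratio as it is, and correction after seeing the data is weaker than a prespecified term.

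The third reply stands: no k or persistence figure is in the documents. The mechanisms that they do support, uptake and a common closing date, correspond to the equal-persistence rows, where the bias is small. Adjustment for indication, if made, would reduce it further.

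A reader might also take the three-week change in the rivaroxaban DVT/PE regimen (section 7) as proof of an early excess shared by both drugs. It is not: it concerns one drug and one indication, and an early excess arising from it would be a real drug effect. What it supports is reporting by band, because the drug effect itself may not be constant.

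**Conclusion.** The point holds as a weakness in a stated method that is cheap to correct. The rate ratio depends on how long each cohort is observed on treatment unless the hazard is flat or the durations match, and the plan secures neither.

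Its size is conditional. Under the assumed threefold early hazard, the bias is negligible to small with equal persistence (about 1.01 to 1.05) and becomes material only with roughly a two-fold or greater difference in persistence, and then mainly if the early period lasts months rather than weeks.

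Three stronger readings are not supported:
- That the bias counts against rivaroxaban. The direction depends on which cohort has the shorter use and on whether the early hazard is higher or lower.
- That the ratio is known to be restricted to current use. Section 9.7.2 does not say so; if all person-time is pooled, the same problem arises through unequal follow-up.
- That a confirmatory test has lost its error control. The Annex 2 checklist records no a priori hypothesis and section 9.5 calls the size calculation preliminary, so the percentages above measure distortion only. The size calculation itself is correct under a constant rate.

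**What to change.** In section 9.7.2:

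- State that the primary rate ratio is for current use.
- Split current-use person-time into prespecified bands of time since index date (for example 0–30, 31–90, 91–180, 181–365 and over 365 days) and include the band as a factor in every Poisson model with drug, age and sex. Cox regression with time since index as the time axis is an equivalent choice.
- Report crude rates and rate ratios by band, so that a drug effect that changes over time can be seen.

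The cost is a short addition to the text and person-time splitting in the existing SAS programs. Index and supply dates are already held, so no new data are needed. The downside is a few extra parameters and few events in the earliest bands; use wider bands for intracranial haemorrhage.

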9.3 Variables

9.3.1 Patient characteristics and drug utilization

Descriptive variables of drug utilization will be presented only for the subpopulation captured by both the outpatient pharmacy database and the GP database, as only in this subpopulation sufficient information for the assignment of the indication of use is available. The following characteristics, including risk factors/potential confounders for the outcomes under study, will be presented for comparison between the two cohorts:

- age and sex distribution at index date 
- dose of index drug at index date (not available for vitamin K antagonists as dosing is determined in anticoagulation clinics) 

- dispensed amount (can be used to estimate duration of treatment) ✓
- where available based on hospital discharge diagnosis or from available GP notes, diagnosis associated with the prescribing of the index drug (where not available, dose and duration of index drug will be used as a proxy for the associated diagnosis among rivaroxaban users). Hospital discharge diagnoses and procedures will be identified within 4 weeks before until 7 days after the index date and GP diagnosed will be identified during the index month or in the month before the index date.
- proportion of patients defined as naïve, non-naïve, recent switchers and distant switchers ✓
- number of pregnant women at index date (if communicated by midwife or gynaecologist) ✓
- number of pregnancies after index date (if communicated by midwife or gynaecologist) ✓
- type of other anticoagulant use before the index date among the non-naïve group ✓
- use of specific prescribed medications both in the year before the index date and following the index date, confirming the ACS indication: antiplatelet drugs (low-dose acetylsalicylic acid, clopidogrel, dipyridamole, prasugrel, ticlopidine and ticagrelor); ✓

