- use of other medications both in the year before the index date and following the index date: anticoagulants (including dabigatran etexilate and apixaban), antiarrhythmic drugs, antihypertensive drugs, statins, anti-diabetic agents, non-steroidal anti-inflammatory drugs, oral corticosteroids, acid-suppressive drugs, disease-modifying anti-rheumatic drugs, antidepressants, antipsychotic drugs, oral contraceptives, hormone-replacement therapy, strong inhibitors of either cytochrome P450 3A4 or P-glycoprotein (e.g. the systemic azole antimycotics ketoconazole, itraconazole, voriconazole and posaconazole and the HIV-protease inhibitor ritonavir), strong CYP3A4 inducers (e.g. rifampicin, phenytoin, carbamazepine or phenobarbital) and fluconazole. ✓
- renal status (estimated glomerular filtration rate [eGFR] or creatinine clearance [CrCl] to be obtained where available, and time of measurement relative to index date). Renal status to be defined as: normal renal function (CrCl > 80 mL/min); mild (CrCl < 80–50 mL/min), moderate (CrCl < 50–30 mL/min) or severe (CrCl < 30 mL/min) renal impairment and end-stage renal disease (CrCl < 15 mL/min) or requirement for dialysis). ✓
- smoking status and body mass index (BMI) recorded in the year before the index date and following the index date.
- hospital admissions for bleeding (see ICD-9 codes in Annex 3) in the year before the index date.
- healthcare utilization (e.g. hospital admissions) in the year prior to the index date. ✓

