9.7.2.1 Sub-cohorts

The PHARMO Database Network consists of databases which differ in geographical catchment area. Data from GP records and inpatient dispensings are available for different sub-cohorts of the source population, which is based on the outpatient pharmacy dispensing database.

General practitioner data will be used as an additional source for identification of the indication of study drug use in the drug utilization analysis and to identify renal status in the safety analysis.

To determine the renal status of patients primary care information and hospital discharge diagnoses will be used. For the subset of patients with GP data, eGFR values (when available) allow classification of the GFR. In the total subset, ICD-9 hospital discharge diagnoses related to renal impairment will be used (Table 12):

In addition, use or non-use of medication used by patients with advanced renal disease is available. Patients will then be characterised as:

End-stage renal disease

- a code for dialysis (V45.1 or V56) given within one year before index date.

Advanced renal disease

- a diagnosis of chronic renal failure (585) given 3 years or more before index date or
- any diagnosis of renal disease (see list) before index in combination with use of phosphate binding drugs, sodium bicarbonate or erythropoietic drugs within one year before index date.
- not being categorized as end stage renal disease (see above)

Mild renal disease

- any diagnosis of renal disease (see ICD-9 list) before index
- not being categorized as end stage or advanced renal disease (see above)

No renal disease

- none of the above

Grouped by renal status, data will be analysed to determine:

- initial indication for rivaroxaban
- rivaroxaban dose received
- crude incidences (calculated as described above) of primary safety outcomes and outcomes related to effectiveness by renal function and by dose

Inpatient dispensing data will be used to follow patients from the date that rivaroxaban or standard of care is started in hospital. The occurrence of an intracranial haemorrhage, gastrointestinal bleeding or urogenital bleeding during hospitalization will be determined on the basis of discharge diagnoses and, if feasible, medical chart review.

It is likely that a potential misclassification of renal failure will be more pronounced in mild renal failure whereas severe forms of renal failure most likely will be readily identified.

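### Baseline renal status is missing from the adjustment set named for the primary bleeding rate ratios, so a renal difference between the cohorts can bias them

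*Protocol*

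**What the plan says.** Protocol 9.7.2 sets the comparative analysis in two tiers. The base tier reads "Age- and sex-adjusted rate ratios with 95% CIs will be estimated for each of the three adverse outcomes comparing rivaroxaban with standard of care", by Poisson regression. The second tier applies only if the numbers and data are sufficient, and it is enumerated: "adjustment will be made for relevant co-medication (described in the drug utilization section), indication and previous hospitalization for bleeding". Renal status appears in neither.

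Elsewhere the protocol treats renal status as important:

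- Section 9.3.1 introduces its list of baseline characteristics as "including risk factors/potential confounders for the outcomes under study". Renal status is on that list, with eGFR or "creatinine clearance [CrCl] to be obtained where available, and time of measurement relative to index date". So is "healthcare utilization (e.g. hospital admissions) in the year prior to the index date".
- Section 8.2 names reduced renal function as one of three groups for subgroup analysis of the safety and effectiveness outcomes.
- Section 9.7.2.1 does not limit renal classification to GP-linked patients: "In the total subset, ICD-9 hospital discharge diagnoses related to renal impairment will be used". It combines these codes with dispensing of drugs typical of advanced renal disease to form four classes (none, mild, advanced, end-stage), all dated before the index date.

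The stated uses of that class are to tabulate initial indication, dose received, and crude incidences of the primary safety and the effectiveness outcomes.

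**The concern.** The comparison is not randomised. If prescribers take renal function into account when choosing between rivaroxaban and standard of care, and renal disease also affects bleeding, the cohorts differ in a cause of the outcome. Age and sex capture part of that difference but not all of it. A rate ratio that leaves renal status out then carries the remainder.

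The named second tier does not close the gap. The co-medication list in 9.3.1 contains none of the marker drugs used in 9.7.2.1 (phosphate binders, sodium bicarbonate, erythropoietic drugs). Antihypertensive and antidiabetic drugs are related to renal disease only loosely. Crude incidences by renal class describe the strata but do not adjust the ratio.

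The study size in 9.5 is set to exclude a 50% increase in risk. A bias towards 1 would be falsely reassuring, and a bias away from 1 would raise a false signal.

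**Working it through.** **1. Can the covariate be derived in both cohorts?** Sections 9.2 and 9.4 run the outcome analysis in the full rivaroxaban cohort and in the comparator users who also have GP data. Section 9.4 says the outpatient pharmacy database is fully linked to the national hospital register. The renal class needs only hospital codes and dispensings, so it can be built for every patient in both cohorts. eGFR needs GP data and so covers only part of the rivaroxaban cohort.

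**2. The plan's own figure (9.5).** This gives the precision against which to judge a bias.

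- Inputs: 5 events per 1000 person-years; 12,000 and 48,000 person-years; ratio to exclude 1.5. Assumed, because not stated: true ratio 1 and two-sided 5%.
- Expected events: 0.005 × 12,000 = 60 and 0.005 × 48,000 = 240.
- SE of the log ratio: √(1/60 + 1/240) = 0.144.
- Power: Φ(ln 1.5 / 0.144 − 1.96) = Φ(0.849) = 0.802.

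The stated 80% reproduces and is not in dispute.

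**3. Size of the possible bias.** For one omitted binary confounder, the rate ratio is multiplied by

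B = [1 + p₁(R − 1)] / [1 + p₀(R − 1)],

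where p₁ and p₀ are the prevalences of renal disease in the rivaroxaban and comparator cohorts after age and sex adjustment, and R is the rate ratio of renal disease for bleeding. The documents give none of the three; all values below are assumptions.

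| p₁ / p₀ | R = 1.5 | R = 2 | R = 3 |
|---|---|---|---|
| 5% / 10% | 0.976 | 0.955 | 0.917 |
| 15% / 20% | 0.977 | 0.958 | 0.929 |
| 10% / 20% | 0.955 | 0.917 | 0.857 |
| 10% / 30% | 0.913 | 0.846 | 0.750 |
| 20% / 20% | 1.000 | 1.000 | 1.000 |
| 25% / 20% | 1.023 | 1.042 | 1.071 |

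Example: 10% / 30% with R = 3 gives 1.20 / 1.60 = 0.75. A true ratio of 1.5 would then appear as 1.5 × 0.75 = 1.125. At the other end it would appear as 1.5 × 1.071 = 1.61.

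Against the SE of 0.144, B = 0.955 is a shift of 0.046 / 0.144 = 0.3 SE, B = 1.071 is 0.069 / 0.144 = 0.5 SE, and B = 0.75 is 0.288 / 0.144 = 2.0 SE.

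**4. How much would a code-based class remove?** Take 5% / 15% with R = 3: unadjusted B = 1.10 / 1.30 = 0.846. Assume the class finds 50% of true cases and has no false positives. Among patients classed as having no renal disease, the hidden prevalence is 0.025 / 0.975 = 2.6% and 0.075 / 0.925 = 8.1%, so the residual B = 1.051 / 1.162 = 0.90. At an assumed 30% sensitivity the hidden prevalences are 0.035 / 0.985 = 3.6% and 0.105 / 0.955 = 11.0%, and B = 1.071 / 1.220 = 0.88. Adjustment helps, but only in part.

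**The case against.** The strongest reply is that the list in 9.7.2 is enumerated but never declared exhaustive. The missing-data text in the same section provides a separate category for potential confounders with missing values and foresees sub-analyses of confounding in complete-data subsets, which would fit eGFR. Section 9.7.2.1 says GP data will identify renal status in the safety analysis. Section 9.7.2.2 allows biases seen in the descriptive part to be dealt with later. A statistical analysis plan, not shown, could name more covariates.

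It stands that the list cannot be called closed. But none of these clauses puts renal status into the rate ratio. The clause in 9.7.2.2 concerns biases that are not expected, whereas renal imbalance is foreseeable. The descriptive comparison is also confined to GP-linked patients, not the full rivaroxaban cohort used for outcomes. Because the protocol names its adjustment set, an analysis plan that follows it would inherit the omission.

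Other points stand in full. The list in 9.3.1 is mixed and labels no single item as a confounder. Section 9.7.2.1 itself expects misclassification of mild renal disease. Earlier admission for bleeding is already in the second tier, and its conditional status is a reasonable guard against sparse events.

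A reader might put prior healthcare use on the same footing as renal status. The documents do not support that without care. Under 9.3.1, indication is itself identified from hospital discharges between 4 weeks before and 7 days after the index date. A covariate for any admission in the previous year could therefore largely mark the index event, especially in ACS and DVT/PE.

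**Conclusion.** The point holds as an avoidable gap in the named adjustment set. Renal status is recorded at baseline, can be derived in both cohorts, and is left out of both tiers of the primary model.

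A reader might go further and infer that the rate ratios are biased by renal channelling, or that the bias favours rivaroxaban. The documents support neither. They contain no renal prevalence by cohort and no association between renal disease and bleeding. Under the assumed grid the factor runs from about 0.75 to 1.07; it is below 1 if renal disease is commoner among comparator users, above 1 if commoner among rivaroxaban users, and exactly 1 if the mix is equal. Nor should the grid be read as the gain from the fix, since a class built on hospital codes removes only part of the confounding.

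The calculation treats renal status as one binary factor with a common effect on bleeding, and takes the prevalences as those left after age and sex adjustment.

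**What to change.** In section 9.7.2:

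- Add the pre-index renal class of 9.7.2.1 to the pre-specified adjusted Poisson model for the three primary bleeding outcomes.
- Report the age- and sex-only ratio beside the adjusted one, so that the effect of adjustment is visible.
- Add a sensitivity analysis adjusting for eGFR in the GP-linked patients of both cohorts.
- Add prior healthcare use only as a secondary covariate, and only if it leaves out the admission that defines the indication (the window from 4 weeks before to 7 days after the index date).

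The cost is a wording change and a few model terms on a variable the plan already derives; no new data are needed. Intervals may widen slightly for the sparsest outcomes. Some confounding by uncoded, mostly mild, renal disease will remain and should be listed in section 9.9.
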